**Table 2 Description of study visit.**

### 13. Data

Data will be collected by the study investigator and/or a research nurse.

#### 13.1 Anthropometric measurements

BMI is calculated as weight in kilograms divided by the square of height in meters. Waist circumference is defined as the widest circumference at the midpoint between the lateral iliac crest and the lowest rib margin at the end of normal expiration. Hips circumference is defined as the widest circumference over the femoral heads.

#### 13.2 Urine sample

Each participant will be asked to provide an early morning urine sample. Urine samples will be frozen at -20°C until analysed. Samples will be stored at University Hospital Coventry. Urine samples will be used to measure markers relating to PCOS, OSA, obesity and components of the metabolic syndrome, such as urinary isoprostanes which are markers of oxidative stress (Patrono and FitzGerald 1997). Urinary isoprostanes, 8-iso PGF2α, will be measured by ELISA using urinary isoprostane EIA kit (Oxford Biomedical Research, Oxford, USA) as per manufacturer's protocol by an operator who is blinded to study group of participants.

#### 13.3 Blood sampling

The study visit and blood sampling will be performed at the follicular phase of the cycle, unless women are oligomenorrhoeic where a random blood sample will be collected. Around 40ml of blood will be collected after an overnight fast. Blood samples will be centrifuged immediately and the serum and plasma aliquots are stored at -80°C till batch analysis. Blood samples will be stored at University Hospital Coventry. Samples will be used to measure markers relating to PCOS, OSA, obesity and components of the metabolic syndrome, such as markers of inflammation (hCRP), IR (FPG, insulin and HOMA-IR), hyperandrogenism (TT, sex hormone binding globulin, free androgen index, androstenedione, and dehydroepiandrosterone sulphate), diabetes (FPG and HbA1C), lipids (total cholesterol, low density lipoprotein, high density lipoprotein, and triglycerides), and reproductive hormones (FSH, LH, oestradiol, Anti-Mullerian Hormone). Participants will be given a

blood form to have their day 21 progesterone measured, unless if oligomenorrhoeic where a random sample will be measured. Participants on the combined oral contraception pill (OCP) will not have their reproductive hormones measured.

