## 8. Study aims

Primary outcome:

- To examine if OSA is associated with impaired QoL in women with PCOS.

Secondary outcomes:

- To assess the relationship between OSA and body composition, hirsutism (modified Ferriman-Gallwey score), period cyclicality, reproductive outcomes, insulin resistance (HOMA-IR), hyperandrogenism, depression and anxiety, FPG, glycated haemoglobin (HbA1C), reproductive hormone profile, lipids, and inflammation (high sensitivity C-reactive protein, hCRP) in women with PCOS.

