### 10.3 Exclusion criteria

- Pregnancy or breastfeeding women.
- Patients who are unable to give consent.
- Patients known to have OSA treated with CPAP.

- Anyone under the age of 18 years.
- Unable to adequately understand or speak English.

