### 13.5 Clinical history

**Period cyclicity:** Women will be asked to estimate how many periods they had in the four months preceding the study visit. We accept that there is a risk of recollection bias with this method. For participants using hormonal contraception, this information will not be collected.

**Hirsutism:** This will be assessed using the modified Ferriman-Gallwey score (Appendix). The modified Ferriman-Gallwey scoring system (Ferriman and Gallwey 1961) is a useful clinical tool, though subjective, in assessing hirsutism. Women are asked to assess the degree of their body hair using pictures of nine body areas and to give a score ranging from 0 (absence of terminal hair growth) to 4 (heavy terminal hair growth) for each area. A total score of 8 or more on the modified Ferriman-Gallwey scoring system is widely considered suggestive of hirsutism (DeUgarte et al. 2006).

**Risk of OSA:** The risk of OSA will be assessed as per clinical practice using the Berlin and ESS questionnaires. Although the ESS (Appendix) is commonly used, it mainly assesses sleepiness (Johns 1991). A score of more than 10 on the ESS is consistent with excessive daytime sleepiness. The Berlin questionnaire (Appendix) assesses the risk of OSA and has a sensitivity of around 85% (Netzer et al. 1999).

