### 14.2 Statistical analysis

Continuous baseline characteristics for each of the PCOS OSA and PCOS low risk OSA groups will be summarised using the mean ( $\pm$ SD) and the median (interquartile range). If the data are approximately normally distributed, the means for the two groups will be compared using the independent t-test. If the data are not normally distributed, the two groups will be compared using the Mann-Whitney U test. Data will be checked for normality using the Shapiro-Wilk test (Razali and Wah 2011). Categorical baseline characteristics for each of the PCOS OSA and PCOS low risk OSA groups will be summarised by reporting the count and percentages in each category. The two groups will be compared using the chi-squared test.

To compare quality of life for the PCOS OSA and PCOS low risk OSA groups, we will fit linear models for each of the primary outcomes of interest (domain scores on the PCOSQ and WHOQOL-BREF questionnaires). The dependent variable in a linear model will be a primary outcome and independent (predictor) variable of interest will be whether a woman is from the PCOS OSA or PCOS low risk OSA group. As the groups may be imbalanced in other predictors for the primary outcomes, the models will adjust for potential confounders such as age, BMI, WHR, use of oral contraceptive pill, ethnicity, education level, marital status, other ongoing illnesses, and parity. Data will be assessed if they are approximately normally distributed; and if they are not, they will be transformed, for example, by taking the logarithm of the outcome variables.

Correlations will be evaluated using Pearson's coefficient (or Spearman's coefficient for non-normally distributed data). A two tailed P value of <0.05 will be considered statistically significant. Statistical analysis will performed using the SPSS statistics package (SPSS Inc., Chicago, USA).

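### As itemised in section 13.3, the combined-pill exclusion does not cover the androgen markers, so pill users enter a secondary hyperandrogenism comparison with no stated adjustment

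*Combined protocol and SAP*

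**What the plan says.** Section 13.3 names its blood markers by group. One group is "hyperandrogenism (TT, sex hormone binding globulin, free androgen index, androstenedione, and dehydroepiandrosterone sulphate"; another is "reproductive hormones (FSH, LH, oestradiol, Anti-Mullerian Hormone". The section closes with the exclusion: "Participants on the combined oral contraception pill (OCP) will not have their reproductive hormones measured". The sentence just before it gives participants a "blood form to have their day 21 progesterone measured, unless if oligomenorrhoeic where a random sample will be measured", and does not mention contraception.

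Section 8 keeps the two groups apart among the secondary outcomes: "hyperandrogenism, depression and anxiety, FPG, glycated haemoglobin (HbA1C), reproductive hormone profile, lipids, and inflammation". Section 10.3, which opens with "Pregnancy or breastfeeding women", does not list contraceptive use as an exclusion.

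For the count of recent periods, section 13.5 uses a wider class: "For participants using hormonal contraception, this information will not be collected". Section 14.2 says that "the models will adjust for potential confounders such as age, BMI, WHR, use of oral contraceptive pill" and further variables, but those are the linear models for the PCOSQ and WHOQOL-BREF domain scores. It states no adjusted model for any biochemical outcome.

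**The concern.** The plan treats pill use as a reason to withhold some hormone values and as a potential confounder for quality of life. The androgen markers get neither protection. The groups are not randomised, and section 14.2 accepts that they may be imbalanced. Entry to sleep testing also depends partly on hypertension or BMI above 30 through category 3 of the Berlin questionnaire. If contraceptive prescribing varies with either, pill use will differ between the groups.

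The outcome matters to the study. Section 6.5 calls the link between OSA and hyperandrogenism controversial, and the hypothesis in section 7 includes more severe biochemical features. If the pill shifts these markers, unequal use biases the comparison, and equal use adds noise or dilutes a real difference.

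**Working it through.** **1. The rules side by side**

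| Outcome | Combined-pill users | Other hormonal contraception | Adjustment stated in 14.2 |
|---|---|---|---|
| Hyperandrogenism markers | measured | measured | none |
| FSH, LH, oestradiol, AMH | withheld | measured | none |
| Progesterone | unclear: not in the itemised list | measured | none |
| Period count | not collected | not collected | none |
| QoL domain scores | kept | kept | pill use |

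No section removes pill users from the first row or adjusts that row for pill use.

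**2. The plan's own figure.** From section 14.1: difference 17.8, pooled SD 18.2, so d = 17.8/18.2 = 0.98; groups of 15 and 23; two-sided 5%. A two-sample t-test (noncentral t) gives 81.9% power, so N=38 reproduces. It is not in dispute. The same split is used below.

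**3. Bias from unequal use, with no true OSA effect.** False difference = (share on the pill in the low-risk group − share in the OSA group) × pill effect. All inputs here are assumptions: mean free androgen index 6.0 off the pill (SD 4) and 1.5 on it, an effect of 4.5 units.
- 10% against 30%: 0.20 × 4.5 = 0.90 units; 0.90/4 = 0.22 SD.
- 10% against 40%: 0.30 × 4.5 = 1.35 units; 1.35/4 = 0.34 SD.
- Standard error of a difference at 15 against 23: √(1/15 + 1/23) = 0.33 SD.

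If use were higher in the OSA group, the sign would reverse.

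**4. The range.** Absolute bias in SD units, and the false-positive rate of an unadjusted t-test (40,000 simulated trials per cell), by assumed pill effect:

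| Pill users, OSA vs low-risk | 0.5 SD | 1 SD | 2 SD |
|---|---|---|---|
| 3/15 vs 5/23 | 0.01; 4.6% | 0.02; 3.5% | 0.03; 1.2% |
| 2/15 vs 7/23 | 0.09; 5.1% | 0.17; 5.6% | 0.34; 6.1% |
| 1/15 vs 8/23 | 0.14; 6.2% | 0.28; 9.8% | 0.56; 18.5% |
| 0/15 vs 9/23 | 0.20; 8.4% | 0.39; 16.8% | 0.78; 42.6% |

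**5. Balanced use.** At 3/15 against 5/23 there is almost no bias, but the extra spread lowers power at d = 0.98 from 82% to 75% (1 SD effect) or 58% (2 SD effect). If instead pill users' values do not differ by group, equal use of 30% shrinks a true difference among non-users to 1 − 0.30 = 70% of its size.

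**6. Cost of restriction**, with equal removal from both groups:

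| Removed | Left | Power at d = 0.98 | Detectable d at 80% power |
|---|---|---|---|
| 0% | 15/23 | 81.9% | 0.96 |
| 10% | 14/21 | 78.7% | 1.00 |
| 20% | 12/18 | 71.9% | 1.08 |
| 30% | 10/16 | 64.5% | 1.18 |
| 40% | 9/14 | 59.0% | 1.26 |

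The value 0.98 is the quality-of-life planning effect and serves only as a yardstick. The plan claims no power for secondary outcomes.

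**The case against.** The narrow reading of the exclusion is not certain. Section 13.3 introduces its groups as examples, and the exclusion directly follows the progesterone sentence although progesterone is not in the itemised list. The authors may have used the term loosely, to include androgens. That is possible, but the itemised list and the separate outcomes in section 8 both point the other way, and staff will work from the list. If the broader meaning was intended, the wording still needs correcting.

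The documents do not say that the pill alters androgen markers, and they give no size or prevalence. This stands: every bias figure above is conditional. The uneven treatment within the plan does not depend on those figures.

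Age, BMI and WHR also go unadjusted in the secondary outcomes, so pill use is one case of a wider gap. That is true, but pill use is the variable that the plan itself treats as grounds for withholding hormone values.

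Dropping women from a study of 38 is costly, and section 14.2 already has pill use as a covariate. This also stands, and it is why an adjusted all-women analysis belongs beside the restricted one.

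**Conclusion.** The point holds as a gap in the handling of a secondary outcome. Following the itemised text, combined-pill users' androgen markers enter a comparison of non-randomised groups with no stated adjustment, while the plan guards against pill use elsewhere. The size is unknown from the documents: near zero bias if use is balanced, about 0.2 to 0.3 SD under the imbalance assumed in step 3, and more only with a larger assumed effect or a more extreme imbalance.

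A reader might infer three stronger things, none of which is supported:
- That the androgen comparison would merely measure prescribing. The bias in step 3 is about one standard error at most, so it would contribute to the result and not replace the comparison.
- That sections 13.3 and 13.5 contradict each other, or that hormone values in users of progestogen-only methods reflect the drug. The two rules concern different variables, and the documents say nothing about the effect of those methods. The difference in scope needs explaining, no more.
- That the main result is at risk. The quality-of-life models already adjust for pill use, and N=38 does not depend on this point.

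**What to change.** In 13.3 and 14.2:
- Make the hyperandrogenism comparison in women not on the combined pill the main secondary analysis.
- Report pill users' androgen values separately by group.
- Add an all-women analysis adjusted for pill use as a sensitivity check.
- Reconcile the combined-pill wording of 13.3 with the hormonal-contraception wording of 13.5, or give the reason for the difference.
- State whether progesterone falls under the exclusion.

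The change is a wording amendment, a filter and one covariate. Sections 13.3, 13.5 and 14.2 already require contraceptive status to be known, so no new visit or sample is needed. The cost is precision in these secondary comparisons: with 20% removed, the standard error rises from 0.33 to √(1/12 + 1/18) = 0.37 SD. The restricted result would also describe only women not on the combined pill.

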#### **11. Recruitment and choosing participants**

##### **– Method of recruitment**

Patients will be given the PIS by the study investigator or clinic nurse while sitting in the waiting area before being seen in the PCOS clinic. They will be advised to take the PIS home and call back if they are happy to take part in the study or if they have any question related to the study. In addition, an invitation letter and study PIS will be sent to patients who attended the PCOS clinic in the last 12 months. A list of patients who attended the PCOS clinic within the last year will be generated and from this list we will identify patients with confirmed diagnosis of PCOS and we will send the PIS and invitation letter to them by post.

Patients will also be recruited from the Weight Management Clinic and the reproductive endocrinology clinic where the PIS will be given to patients with a history of PCOS by the clinic doctor. Patients will be advised to take the PIS home and call back if they are happy to take part in the study or if they have any questions related to the study.

A poster inviting women with a history of PCOS to take part in the study will be displayed at University Hospital Coventry and an e-poster will be displayed at the hospital intranet. Women who answer the advert will be sent the PIS and advised to call back if they would like to take part or if they have any question about the study.

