## 12. Overview of study visit

Patients who agree to take part in the study will be asked to fast for 10 hours, where only water is allowed, before the study visit. Patients will also be asked to avoid exercise, caffeine (for example coffee, tea, and caffeine rich drinks), and chocolate in the 24 hours prior to the study visit; a clear instruction on which foods or drinks to avoid will be provided in the PIS.

On the study visit and after obtaining consent from study participants, their eligibility criteria to take part in the study will be assessed by the study investigator. Participants who fulfil the study inclusion/exclusion criteria will have full medical history obtained, and physical examination performed. If risk of OSA has not already been assessed in the clinic using the Berlin and the ESS questionnaires, these questionnaires will be completed. Participants with a high score on either the Berlin or ESS questionnaires will be provided with a portable sleep machine to take home; and a referral to the respiratory clinic will be arranged as per routine clinical practice. Information on how to use the sleep machine will be explained to the study participant by study doctor. Participants will be asked to return the machine the next day. Participants will have fasting bloods and early morning urine samples collected and stored. They will fill QoL and depression questionnaires. They will also be asked detailed questions about their fertility history. For women with regular periods, this visit will occur at the follicular phase of the cycle (day 1 – 7); while for oligomenorrhoeic women a random blood sample will be collected. The duration of the visit is approximately 1.5 hours.

A summary of patient activity during the study visit is provided in Table 2.

Visit	1
Participants	All
Duration	Approximately 1.5 hours
Informed consent	X
Medical history	X
Reproductive history	X
Anthropometry	X
Physical examination	X
Screening for OSA	X
Early morning urine sample	X
Blood tests	X
QoL and HAD questionnaires	X

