### 13.4 Reproductive history

Participants will be asked if they are currently trying for children. Infertility will be defined as failure to achieve a clinical pregnancy after 12 months or more of regular unprotected sexual intercourse (Zegers-Hochschild et al. 2009).

Participants will be asked if they have tried for children in the past, and if so:

- Number of pregnancies
- Number of children
- Number of miscarriages
- Have they been seen in the fertility clinic?
- Have they required any fertility treatment?
- Have they developed gestational diabetes?
- Have they developed pre-eclampsia or any pregnancy related complications?

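### The rules that withhold hormones and period counts differ from each other and miss non-contraceptive hormonal treatment, so treatment can mimic or hide an OSA difference in two secondary comparisons

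*Combined protocol and SAP*

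**What the plan says.** All references are to the combined protocol and SAP.

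- **Hormones (13.3).** "Participants on the combined oral contraception pill (OCP) will not have their reproductive hormones measured". The panel is given as "reproductive hormones (FSH, LH, oestradiol, Anti-Mullerian Hormone". The androgen markers are listed separately, under hyperandrogenism.
- **Periods (13.5).** "Women will be asked to estimate how many periods they had in the four months preceding the study visit". Then: "For participants using hormonal contraception, this information will not be collected".
- **Eligibility (10.2, 10.3).** The exclusions begin with "Pregnancy or breastfeeding women" and go on to consent, CPAP-treated OSA, age and English. Neither list mentions hormonal or fertility treatment.
- **Recruitment (11).** Besides the PCOS clinic, letters and posters: "Patients will also be recruited from the Weight Management Clinic and the reproductive endocrinology clinic".
- **What is recorded (12, 13.4).** Eligible participants "will have full medical history obtained, and physical examination performed", but no medication item is named. Section 13.4 asks whether a woman is currently trying to conceive. The question "Have they required any fertility treatment" is undated and sits among those put to women who have tried in the past.
- **Analysis (8, 14.2).** Period cyclicity and the reproductive hormone profile are named secondary outcomes. Linear models with covariates are specified for the PCOSQ and WHOQOL-BREF domain scores only. The contraceptive pill is the only drug in the illustrative covariate list.

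**The concern.** The evident reason for both withholding rules is that hormone levels and bleeding under a hormonal drug reflect the drug and not the severity of PCOS. That reasoning does not stop at contraceptives, and it does not differ between hormones and periods. As written, each rule stops at a different place, and neither reaches a woman who takes hormonal treatment for another purpose.

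The sampling schedule adds to this. Under 13.3, women are sampled in the follicular phase unless they are oligomenorrhoeic, in which case the sample is random. A woman whose cycles are regular only because of treatment could be placed on the timed schedule and counted among those with milder disease.

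The hypothesis in section 7 is that women with OSA have more severe clinical and biochemical features of PCOS. At stake is whether a difference, or a lack of one, in these two secondary outcomes can be put down to OSA. The primary quality-of-life question is not at stake.

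**Working it through.** **1. Group sizes.** Section 14.1 gives 38 women, 15 with OSA and 23 at low risk, for 80% power at two-sided 5% with effect size 0.98 and allocation ratio 0.67. With the noncentral t distribution, the control group needs 21.58, rounded to 22. The OSA group needs 0.67 × 21.58 = 14.5, rounded to 15. The total is 37, and power at 15 and 23 is 0.819. The plan's figure reproduces, and nothing here contests it. The 15 and 23 are used below.

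**2. Whom each rule reaches.**

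| Woman's treatment | Reproductive hormones (13.3) | Period count (13.5) |
|---|---|---|
| Combined pill | not measured | not collected |
| Other hormonal contraception | measured | not collected |
| Ovulation induction or other non-contraceptive hormonal treatment | measured | collected |
| None | measured | collected |

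The second row is an inconsistency between the two sections. The third row is a gap in both.

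**3. Whether another part of the plan closes the gap.** Sections 10.2 and 10.3 exclude no one on treatment. Section 14.2 specifies no adjusted model for hormones or periods. Sections 12 and 13.4 may bring some treatment to light, but they give no date and no rule for using the answer.

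**4. Size if use is unequal.** Let p be the share treated in each group and g the effect of treatment in SD units:

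shift = (p in OSA group − p in low-risk group) × g.

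The documents give neither p nor g, so all values below are assumptions. Section 14.2 names no test for these outcomes; an unadjusted t-test is assumed. False-positive rates come from 20,000 simulated trials per row, 15 against 23, with no true OSA effect.

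| g | OSA / low-risk share treated | Shift (SD) | False-positive rate |
|---|---|---|---|
| 0.5 | 10% / 10% | 0 | 5.0% |
| 0.5 | 5% / 20% | −0.075 | 5.6% |
| 0.5 | 0% / 20% | −0.10 | 6.1% |
| 0.5 | 10% / 30% | −0.10 | 5.7% |
| 1 | 10% / 10% | 0 | 5.2% |
| 1 | 5% / 20% | −0.15 | 6.8% |
| 1 | 0% / 20% | −0.20 | 8.2% |
| 1 | 10% / 30% | −0.20 | 7.9% |
| 2 | 10% / 10% | 0 | 5.1% |
| 2 | 5% / 20% | −0.30 | 9.7% |
| 2 | 0% / 20% | −0.40 | 14.6% |
| 2 | 10% / 30% | −0.40 | 13.9% |

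If the OSA group were the more treated, the sign of the shift would reverse.

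**5. The same formula in periods.** Assume that treatment adds 2 periods over four months and that four women are treated. With a split of 3 OSA and 1 low-risk, (3/15 − 1/23) × 2 = 0.157 × 2 = 0.31 periods. With 1 and 3, (1/15 − 3/23) × 2 = −0.064 × 2 = −0.13 periods.

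**6. Imbalance by chance alone.** If treatment is unrelated to OSA, the number treated in the OSA group is hypergeometric. With four treated among 38, splits of 0, 3 or 4 in the OSA group give an imbalance of at least 10 percentage points. The probability is (8,855 + 10,465 + 1,365) / 73,815 = 28%. With 2, 6 and 8 treated it is 15%, 37% and 44%.

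**The case against.** The strongest reply is that nothing shows harm. The documents do not say that any participant will be on ovulation induction, still less that use differs by OSA status. With equal use there is no shift and the false-positive rate stays at about 5%. With unequal use and a modest effect of 0.5 SD it reaches only about 6%. This stands: a reader might infer that treatment will be read as an OSA difference, but the documents support only that it can be.

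A second reply is that the information is not lost. Section 12 takes a full medical history, and a woman already on ovulation induction has normally tried to conceive before, so the fertility-treatment question in 13.4 may well reach her. This also stands. A reader might infer that treated women could never be identified afterwards; the text does not go that far. What is missing is a dated item on current treatment and a rule for its use.

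Third, a reader might want the bias in hormone units. That needs treated and untreated levels that the documents do not give. Nor can all untreated women be taken as anovulatory: section 10.2 requires only two of three Rotterdam features, and section 12 plans for women with regular periods. The direction is open too. If heavier women had less access to treatment, the OSA group would be the less treated, but the documents do not say so.

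Fourth, leaving treated women out has a bias of its own, because they may be those with worse ovulatory dysfunction. This is a fair objection to exclusion alone, and it is why the fix reports both analyses.

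None of these replies removes the mismatch between 13.3 and 13.5 or brings non-contraceptive treatment under either rule.

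**Conclusion.** The concern holds as a gap in the rules for two secondary comparisons. Hormones are withheld for the combined pill only and periods for hormonal contraception only. Other hormonal treatment is neither excluded, nor recorded as a dated item, nor adjusted for. If use differs between the groups, by chance or through weight, treatment can be taken for an OSA difference or can conceal one. If use is equal, it adds noise only.

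The size is unknown. The calculations show how the shift scales with assumed shares and effects, and that with 38 women a handful of treated participants can be unevenly split by chance. They do not estimate the bias in this study.

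A reader might extend the point to the main result, but the documents do not support that. The hormone and period rules play no part in the quality-of-life comparison or in the sample size calculation. Severity is minor, and the change is worth making because it is cheap.

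**What to change.** - **Record.** Add one item to the visit form: hormone-altering treatment, contraceptive or other, current or within the four-month period window, with dates.
- **Align.** Reword 13.3 and 13.5 so that both cover the same women: users of any hormonal contraception and women on other hormone-altering treatment.
- **Analyse.** In 14.2, state that the main reproductive-hormone and period-count comparisons leave treated women out, and that each is repeated with them included as a sensitivity analysis. For that repeat to be possible, samples and period counts from women on non-contraceptive treatment must still be collected, so for them the rule governs analysis and not collection.

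The cost is one question and a sentence in each of the three sections. The downside is a few women lost from the main version of two secondary comparisons. No one's care changes, treated women stay in the primary quality-of-life analysis, and the sample of 38 stands.
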